The Unified Parkinson's disease Rating Scale - Part III (UPDRS-Part III)^{75, 76} and the modified Hoehn and Yahr Rating Scale (HYRS)^{77, 78} will be used to assess level of motor impairment and disease severity. For this assessment participants go through a series of tasks designed to assess various motor characteristics such as speech, facial expression, rigidity, finger tapping, hand movements, toe tapping, freezing of gait, balance, etc. We will also use UPDRS item #13 to assess fall risk (please see Monitoring Plan below). These are standard instruments for measuring the motor symptoms and disease severity in patients with PD and have been used extensively in both research and clinical settings. VASDHS/UCSD neurologists will perform these assessments immediately prior to the cognitive assessment at the pre and 12-month follow up evaluations.

Adjunct Performance Measures:

Motor Skill Fitness measures will be carried out by a trained research assistant at the VA Medical Center

Subjects will undergo body mass index analysis at the VA Medical Center

De-identified data from these Motor Skill Fitness measures will be analyzed in the Smart Lab at UC San Diego. No participant data will be collected there.

Client Satisfaction with the intervention will be assessed at the end of the intervention with the Client Satisfaction Questionnaire (CSQ-8)⁷⁹. The CSQ-8 is an 8-item, 2-3 minute measure that yields a single score, ranging from 8 to 32 (each item rated on a 4-point Likert scale), with higher scores indicating greater satisfaction. The CSQ-8 has been widely used in clinical research trials and is reported to have excellent reliability and internal consistency, acceptability to clients and service providers, and sensitivity to different levels of program quality.

Intervention: The treatment intervention is CogSMART-PD. Participants will meet in groups of 5 individuals per group for 1.5 hours once per week for 10 weeks.

Control Group: The supportive care (control) group will entail having groups of 5 individuals with PD-MCI meet for peer-support for 1.5 hours once per week for 10 weeks. A trained clinician will serve as the facilitator of this group and will be instructed to not provide any treatment or intervention strategies. The main role of the facilitator will be to create a safe and respectful environment where members feel comfortable sharing their knowledge and insight with each other.

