Monitoring Plan. As individuals with PD are at high risk for falls, we will carefully screen all individuals for history of falls upon recruitment. We will use the baseline UPDRS falling item (#13) in which a history of falls is categorized on a likert scale from 0 (none) to 4 (falls >once per day). A history of falls as assessed by the UPDRS appears to be one of the best predictive methods of subsequent falls at this time⁸⁰. Those individuals who endorse a history of falling or score >0 on the UPDRS falling item, will be closely monitored. This includes ensuring that they are escorted to and from the intervention room from their vehicle as well as to and from the bathroom, as needed. Should a patient need help within the bathroom,

a caregiver will be requested to assist. If needed, we will utilize the VA escort service. Although not common in PD, all participants will also be assessed for suicidal ideation/intent at baseline, as standard of care for psychological/behavioural interventions. If suicidal ideation is acknowledged, indicated by a score of 2 or greater on item 9 of the Beck Depression Inventory-II (BDI-II), research participants will be referred directly to a VA-privileged clinician for further evaluation. These participants will be monitored for changes in mood during the intervention.

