such information arise that causes study staff to be concerned about that participant's psychological well being, appropriate referrals to the VASDHS Geropsychiatry Clinic or other appropriate community referrals will be made. As individuals with PD are at a high risk for falls, we will carefully screen all individuals for history of falls upon recruitment. We will use the baseline UPDRS falling item (#13) in which a history of falls is categorized on a likert scale from 0 (none) to 4 (falls >once per day). A history of falls as assessed by the UPDRS appears to be one of the best predictive methods of subsequent falls at this time. Those individuals who endorse a history of falling or score >0 on the UPDRS falling item, will be closely monitored. This includes ensuring that they are escorted to and from the intervention room from their vehicle as well as to and from the bathroom, as needed. Should a patient need help within the bathroom, a caregiver will be requested to assist. If needed, we will utilize the VA escort service. Although suicide is an extremely minimal risk factor for PD patients, suicidal ideation/intent will be assessed at baseline. Any indication of suicidal ideation will be brought to licensed and privileged supervisor's immediate attention. All intervention group participants will be provided with the class manual and so if there is a need for early termination with no opportunity to join another group, those individuals will still have the psychoeducation materials. In general, the study poses no significant increase in risk than what would normally be present in proper clinical management and psychological treatment of PD-MCI patients.

A tertiary risk might include unintentional disclosure of confidential test information, but confidentiality will be strictly maintained in data storage, manipulation, and presentation. Participant identity will be coded immediately upon entry into the study, and neither the participants' names nor any identifying information will be present in the data set. Presentation of the results will involve group data and the subjects' identity will not be disclosed.

MRI neuroimaging

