For those individuals who participate in the Wii adjunct program, there is an increased risk of physical injury, frustration and/or physical fatigue during the sessions. However, the Wii program is a low-exertion physical activity that only involves upper body (arm) movements. For those at risk of falling (as indicated by medical chart), we will have these patients sit in a chair while performing the Wii activities. Breaks and water will be frequently offered throughout the 30-minute session to prevent physical fatigue, frustration, and/or dehydration.

Odoroki participation

For those individuals who participate in the Odoroki adjunct program, there is an increased risk of physical injury, frustration and/or physical fatigue during the sessions. However, the Odoroki program is a low-exertion physical activity. For those at risk of falling (as indicated by medical chart), we will have these patients sit in a chair while performing the physical activities. Breaks and water will be frequently offered throughout the 60-minute session to prevent physical fatigue, frustration, and/or dehydration.

Saliva Sample

There is no identifiable bodily risk in taking a saliva sample beyond that of an ordinary medical examination; there is potential of small discomfort a mild scraping with a swab of the inside of the cheek to obtain the sample, and subjects that provide a saliva sample may experience dry mouth or difficulty producing saliva. Suggestions for improving saliva generation will be provided. The saliva sample will not be banked and, instead, the sample will be destroyed after processing.

Section 15 - Risk Management

15) Describe the procedures for protecting against or minimizing any potential risks/discomforts, and the adequacy of resources for conducting the study and resources participants may need as a consequence of the research. When applicable, include detail of the following safety measures: (a) The type of safety information to be collected, including AEs; (b) Frequency of safety data collection; (c) Frequency or periodicity of review of cumulative safety data; (d) Statistical tests for analyzing the safety data to determine if harm is occurring; and (e) Conditions that trigger an immediate suspension of the research. See ? for further requirements.

Phase I:

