Test anxiety, boredom and fatigue will be minimized by explaining the testing procedures, by supportive assurance, and by taking brief rest periods throughout the two-2.5 hour evaluation. Evaluations will be performed by examiners experienced in working with geriatric and neurologic populations and will be able to gauge when breaks are needed or when testing may need to be rescheduled or cancelled due to severe fatigue or anxiety. To minimize potential discomfort during the UPDRS motor exam, study staff will briefly explain the nature and purpose of the exam before beginning, and will instruct subjects to ask questions or communicate if they are unsure about or uncomfortable with any portion of the exam. Additionally, subjects will sign and receive a copy of the consent addendum, which has further details about the exam, prior to the exam. Each CogSMART-PD session will last approximately 1.5 hours and breaks are offered throughout the session as well. As individuals with PD are at a high risk for falls, we will carefully screen all individuals for history of falls upon recruitment. We will use the baseline UPDRS falling item (#13) in which a history of falls is categorized on a likert scale from 0 (none) to 4 (falls >once per day). A history of falls as assessed by the UPDRS appears to be one of the best predictive methods of subsequent falls at this time. Those individuals who endorse a history of falling or score >0 on the UPDRS falling item, will be closely monitored. This includes ensuring that they are escorted to and from the intervention room from their vehicle as well as to and from the bathroom, as needed. Should a patient need help within the bathroom, a caregiver will be requested to assist. If needed, we will utilize the VA escort service. Although not common in PD, all participants will also be assessed for suicidal ideation/intent at baseline, as standard of care for psychological/behavioural interventions. If suicidal ideation is acknowledged, indicated by a score of 2 or greater on item 9 of the Beck Depression Inventory-II (BDI-II), research participants will be referred directly to a VA-privileged clinician for further evaluation. These participants will be monitored for changes in mood during the intervention.

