
Discomfort during imaging sessions will be minimized with attention to cushioning the subject's head, neck, shoulders and knees such that the patient may fully relax and not hold any tension to maintain position within the bore of the magnet. The patient is free to move about except during the approximately ¾ hour's imaging time. Subjects will be told before being placed in the bore of the magnet that they may experience claustrophobia or other discomfort while in the magnet and that they should report this via the intercom as soon as they feel the need to be removed, in which case imaging personnel will remove them immediately. Subjects will be told they are free to terminate the study at any time at no detriment to themselves or to any care they may be receiving from the VA. The risk of imaging subjects with metal in their body, or who have pacemakers, will be eliminated by screening using a standard MRI screening form. This instrument has been used successfully in past protocols to exclude patients with suspected or known risk factors. This screening form is administered over the telephone when making the MRI scan appointment and again independently on the day of scanning. If the screening form elicits any suspected risk factors, the form will be supplemented by review of medical records with the subject's permission. Finally, subjects will be asked the screening questions one more time by the MRI technician before being

placed in the magnet and will be apprised of the risks as part of signing the consent form.

Wii participation:

Wii games will be restricted to those requiring upper body movements (e.g., tennis, ping pong, and golf). For those at risk of falling (as indicated by medical chart), we will have these patients sit in a chair while performing the Wii activities. Breaks and water will be frequently offered throughout the 30-minute session to prevent physical fatigue, frustration and/or dehydration.

Odoroki participation:

For those at risk of falling (as indicated by medical chart), we will have these patients sit in a chair while performing the Odoroki activities. Breaks and water will be frequently offered throughout the 60-minute session to prevent physical fatigue, frustration and/or dehydration.

Saliva sample:

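### In Phase II, the rule to seat fall-risk participants during Odoroki and Wii sessions looks only to the medical chart, not to the study's own baseline fall screen (UPDRS item 13 or reported falls).

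*Combined protocol and SAP*

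**What the plan says.** Two rules in the Phase II text deal with fall risk.

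**Screening and monitoring.** Section 9 (PD Motor and Disease Severity Assessment) states "We will also use UPDRS item #13 to assess fall risk". The Monitoring Plan that follows sets the threshold and the response: "Those individuals who endorse a history of falling or score >0 on the UPDRS falling item, will be closely monitored". The response it spells out begins "This includes ensuring that they are escorted to and from the intervention room from their vehicle" and goes on to bathroom escort and caregiver help. Sections 14 and 15 repeat this plan for Phase II. Section 15 promises that "we will carefully screen all individuals for history of falls upon recruitment", and Section 14 justifies the instrument: "A history of falls as assessed by the UPDRS appears to be one of the best predictive methods of subsequent falls at this time".

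**Seating during adjunct exercise.** Section 14, under Odoroki participation, provides for people at risk of falling "as indicated by medical chart), we will have these patients sit in a chair while performing the physical activities". Section 15 repeats it in nearly the same words ("we will have these patients sit in a chair while performing the Odoroki activities"), again with the chart as trigger. The Wii paragraphs of both sections do the same.

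Section 9 plans 8-10 Odoroki participants with 20 one-hour sessions, and 8-10 Wii participants with ten sessions of 30 minutes. It says both groups are assessed in the same way as the other CogSMART participants.

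**The concern.** The protocol has two working definitions of a person at risk of falling. It uses the one it ranks among the best predictors to decide who is escorted along a corridor. For the exercise itself, which Section 14 says raises the risk of physical injury, it uses only the other. Someone whom the study has just identified as a faller may not meet the written condition for sitting down.

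This is a question of participant safety and concerns Odoroki most. Wii is confined to arm movements. Odoroki carries no such limit; Section 14 says only that "the Odoroki program is a low-exertion physical activity". The Phase II background in Section 7 describes it as physical activity that engages the vestibular, proprioceptive and motor systems while the participant also does mental work.

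**Working it through.** No sample size, power or error rate is involved, so the check is a comparison of text followed by a bound on the number of people.

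**Step 1. Set the Phase II statements side by side.**

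| Statement | Where | Trigger | Action |
|---|---|---|---|
| Monitoring | Section 9, Monitoring Plan | reported falls or item 13 above 0 | close monitoring, escort |
| Monitoring | Section 14, Phase II | same | same |
| Monitoring | Section 15, Phase II | same | same |
| Wii seating | Section 14 | medical chart | sit |
| Odoroki seating | Section 14 | medical chart | sit |
| Wii seating | Section 15 | medical chart | sit |
| Odoroki seating | Section 15 | medical chart | sit |

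All 4 seating statements name the chart alone, and 0 of 4 mention item 13 or reported falls. None of the 3 monitoring statements mentions seating or the adjunct sessions.

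**Step 2. Is the screening result available for these participants?** Yes. Section 9 gives adjunct participants the same assessments, so item 13 and fall history exist at baseline.

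**Step 3. Must the result reach the chart?** No. Sections 27.b and 27.b1 provide for CPRS notes for people who attend treatment sessions, so it could be recorded there. Nothing requires item 13 to be entered, or the chart to be checked for it before a session.

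**Step 4. Could a chart be silent on falls?** It is plausible. Sections 10 and 10.1 allow Phase II recruitment from UCSD, other hospitals, private practices and the community, so VA chart history may be thin for some participants. The 15-question telephone screen for outside referrals (Section 12.10a) has no question on falls. The documents give no rate.

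**Step 5. Bound the size.**

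- Odoroki: 8-10 participants, so 0 to 10 affected.
- Both programs, assuming separate people: at most 10 + 10 = 20, so 0 to 20 affected.
- Per affected person, Odoroki: 20 sessions × 1 h = 20 h.
- Per affected person, Wii: 10 sessions × 0.5 h = 5 h.

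The upper limits are simply the planned group sizes. The hours are the full program length without a written seating requirement, not a measure of risk.

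**The case against.** The strongest reply has three parts.

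*Monitoring is not limited to escorts.* The listed measures are introduced as inclusions, so staff who know a participant has fallen may watch that person during exercise and offer a chair. This stands as a partial safeguard. It leaves sitting to discretion, however, while the protocol has a specific seating rule that directs staff to the chart.

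*The two triggers may overlap.* Neurologists perform the motor assessment, participants authorize access to their records, and progress notes are foreseen. The gap needs a person who reports falls, has a chart silent on them, and is left standing. The documents do not show that such a person will exist, and the number may be zero. Nor do they require anything that would close the gap.

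*Different thresholds can be deliberate.* A score above 0 on a 0-4 scale is a low bar. It suits a light measure such as an escort, whereas sitting changes the activity under study. Because the protocol describes people with Parkinson's disease as being at high risk of falls, the wider trigger could seat more than a few of the 8-10 in Odoroki. That cost is real. But nothing in the text says the difference was intended, and the sponsor already accepts seating for fallers identified from the chart.

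It is also true that the motor assessment includes balance and freezing of gait, and that Section 9.8 lists a falls efficacy scale. Neither is tied to seating.

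**Conclusion.** The concern holds. The Phase II seating rule rests on the chart alone and is not connected to the fall screen that the study performs on the same people. It should be corrected, but its reach is limited: two small exploratory adjunct groups, a partial safeguard already in place, and no effect on the primary analysis. The number affected lies between 0 and 10 in Odoroki, or 0 and 20 with Wii, and cannot be narrowed because the documents give neither an item 13 distribution nor a rate of charts silent on falls. The conclusion about the wording is firm. The safety consequence depends on at least one adjunct participant having a positive screen and a silent chart, which is plausible but not shown.

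**What to change.** In Sections 14 and 15, Phase II, change the trigger in the Wii and Odoroki paragraphs to: *as indicated by the medical chart, an endorsed history of falls, or UPDRS item 13 >0*. If the sponsor thinks a score above 0 is too low for mandatory seating, a higher stated score with its reason would also remove the inconsistency.

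The change is wording in four places. It needs no new assessment, because item 13 and fall history are already collected at baseline. The cost is that an unknown number of additional participants (0-10 in Odoroki) would exercise seated, which could weaken the exploratory comparison of motor skills under Exploratory Hypothesis 3. In a group of 8-10 people, fall protection should take precedence over that comparison.

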Saliva samples will be stored at and analyzed by the UCSD Integrative Health and Mind-Body Biomarker Laboratory, located at the Medical Teaching Facility, Room 431. Samples are de-identified, and are destroyed after analysis.

In the submission form, upload a copy of the grant, subaward, CRADA, etc. as applicable to the study.

Section 27 - Privacy, Confidentiality, and Information Security

27a) Provide a brief description of how participant privacy and confidentiality will be protected in this study. Describe the circumstance under which it may be possible for a research team member to identify subjects and any related protections or assurances to prohibit or avoid identification. Describe how the number of people with access to identifiers for research purposes is limited in order to protect a participant's privacy.

All data used in the study will be de-identified and linked to SI by an identifier number. SI will remain in a locked filing cabinet in the PI's lab space in building #13, separate from the de-identified data files, and will only be accessible by approved study personnel.

In the groups, which are audio recorded, subjects are asked to call each other only by first name, to help avoid confidentiality breach.

In the event of a real or suspected breach of security, the VA Police, VA Information Security Officer, and VA Privacy Officer will be notified.

Study records entered into a computer system will be assigned code numbers and will not be individually identifiable.

27.b) Entry of a CPRS Research Informed Consent Note is required when subjects will be admitted as inpatients or treated as an outpatients for research and the study involves research medical care or may affect medical care.

- *If a Research consent Note is required, then a Research Progress Note should also be entered for each procedure or intervention.*
- *Scanning the Consent and HIPAA Authorization into CPRS is not required. Linking the Consent to the Research Informed Consent Note may be permitted and can be useful for trials involving the Research Pharmacy or when research will be performed in conjunction with clinical procedures.*
- *For Non-Veterans, if Research Informed Consent Notes are entered, then the NOPP Acknowledgment must be scanned into the record. Otherwise a copy of the signed NOPP must be retained with the Investigator's research records and a copy sent to the Privacy Officer; see the ? Help for more information.*

27.b1) Is entry of CPRS notes required based on the above criteria?

CPRS notes are needed for ALL subjects
 CPRS notes are needed for SOME subjects
 CPRS notes are NOT needed for any subjects

Identify for which group or groups CPRS records will be entered and to which groups this requirement does not apply.

CPRS notes will be entered for individuals who are consented and attend the treatment sessions. Caregivers who are enrolled into the study do not need CPRS notes because they do not attend treatment sessions nor receive any treatment. Additionally, there are cases where individuals consent to be in the study and complete neuropsychological assessments to determine eligibility but do not end up enrolling into group due to various reasons such as not being able to commit to the 10-week group, loss of interest, etc. In those cases, they do not attend the first day of group and do not receive any treatment; therefore, CPRS notes would not need to be entered for those individuals.

27c) Select the VA Sensitive Information (VASI) use category

This study does not collect or use any VASI
 This study uses but does not save, collect, copy, or record VASI
 This study does collect or record VASI

Section 27.1 VA Sensitive Information (VASI)

27.1a) For each type of VASI, indicate all that apply:

Indicate which of the following will be collected/recorded:

- Protected Health Information (PHI)
- Names
- Device identifiers and serial numbers
- E-mail addresses
- Medical record numbers
- URLs (Universal Resource Locator)
- All elements of dates (except year) or any age over 89
- Health plan beneficiary numbers
- IP Addresses (Internet Protocol)
- Telephone numbers
- Account numbers
- Biometric Identifiers including finger and voice print
- Fax numbers
- Certificate or license numbers
- Full face photographic images and comparable images
- All geographic subdivisions smaller than a state
- Vehicle ID and serial numbers including license plate numbers
- Social security numbers or scrambled SSNs (describe below)
- Other unique identifying number, characteristic, or code (describe below)

27.1a1) Describe why SSN are needed for this study

SSN are needed for subject payment

27.1b) Consent Forms and/or HIPAA Authorization

Yes No

27.1c) Images with personal identifiers are used for this study (x-rays, MRI images with patient names, record numbers, dates, etc.)?

Yes No

27.1d) Photos with faces or audio video recordings are used for this study.

Yes No

27.1d1) Identify the device or devices that will be used to take/make the photographs or recordings.

An audio recorder will be used to record group interventions to assess treatment fidelity.

27.1d2) Identify where images will be stored (e.g., in the medical record, with study hardcopy records, with study electronic VASI records

Audio recordings will be transferred to a computer system and assigned group numbers, and will not be individually identifiable. The key relating group numbers to the individuals will be stored separately, protected by strong passwords, and accessible only by approved study personnel.

27.1e) Biological specimens with identifiers are used for this study.

Yes No

Section 27.2 Data Collection, Tools, and Resources

27.2a) Will any specially obtained software be used?

Yes No

27.2b) Will any mobile devices (laptop, tablet, portable hard-drive, etc.) be used in support of this study?

Yes No

27.2c) Does the study require use of an electronic data capture system?

Yes No

27.2d) Will any other web-based applications be used (e.g., for recruitment, completing online questionnaires, or processing data)?

Yes No

27.2e) Will coded data that excludes personal identifiers be used? Coded data excludes *all* HIPAA identifiers (per VHA Handbook 1605.1 Appendix B), including dates

Yes No

Section 27.3 Data Sharing and Transportation

27.3a) Does this study involve collecting, sharing or transporting any type of data outside of the local VA?

Yes No

27.3b) This study collects VASI outside of VA (i.e., at a non-VA location).

Yes No

27.3c) VASI is transported outside of VA for any purpose other than sharing.

Yes No

27.3d) PHI may be disclosed to monitoring/auditing agencies by HIPAA Authorization. Note: The Research Office must be notified when monitors come to audit

Yes No

27.3e) Data may be shared with collaborators or others in the conduct of this protocol.

Yes No

27.3e1) Describe the data to be shared or disclosed, the entities to which the data are to be disclosed, how the data are to be transmitted, and how the transmitted data will be stored, retained, destroyed, and/or further disclosed and to whom. This includes data from individual subjects as well as other data developed during the research such as the analytic data and the aggregate data. For PHI and VASI, indicate the authority/ies permitting the sharing or disclosure of data (HIPAA Authorization, Limited Data Set, Data Use Agreement, VA Form 10-5345-Request for and Authorization to Release Health Information., etc.).

De-identified data may be shared to be analyzed by the Smart Lab at UC San Diego. This de-identified data will be sent via encrypted email, and while being analyzed will be stored in a standalone (non-networked), password-protected computer in the Smart Lab at UCSD. No participant data or identifying data will be collected at the Smart Lab, and no identifying data will be stored there.

Section 27.4 Research Record Storage and Retention

For each type of record, indicate whether it is collected for this study

27.4a) Hardcopy records/data (includes paper, pictures, film, etc.)

Yes No

27.4a1) Identify precisely where hardcopy data will be stored to include physical site, building, and room number, etc. For each location identify whether VASI or non-sensitive information is stored at that location. For VASI, identify how the data is secured.

Neuropsychological tests, administered in a pencil-and-paper format, will be administered and recorded answers will be stored in the PI's lab space (rooms 330, 332, and/or 306B) in building 13.

27.4a2) Are all of the above locations at VA?

Yes No

27.4b) Electronic study records (includes computer files, removable disk files, digital files, etc.).

Yes No

27.4b1) Identify precisely where **non-sensitive** electronic records/data will be stored to include the full map drive, network location/server name, etc., and a brief description of what data/information is stored at each location.

Audio recordings of the intervention meetings will be transferred to the VA computer R drive so that investigators may assess treatment fidelity, and all audio files will be destroyed at the end of the study.

27.4b2) Identify precisely where **VASI** electronic records/data will be stored to include the full map drive, network location /server name, etc., and a brief description of what data/information is stored at each location.

If no VASI is collected or recorded for this study, simply indicate that the “Study does not collect or record VASI”.

Study does not collect or record VASI

27.4b3) Are any of the locations described in 27.4b outside of the VA Secure Network? *Note: this includes storage on a computer local hard drive.*

Yes No

27.4c) Record Retention - VHA requires compliance with Records Control Schedule (RCS-10) for retention of electronic and hard copy records. Following study closure, these temporary records must be retained for six years and then destroyed. Longer retention may be permitted if required by other Federal regulations or requirements. Will RCS-10 requirements be followed (i.e., 6-year retention)?

I will adhere to VHA Records Control Schedule-10 requirements
 I request an exception to RCS-10 requirements

Section 27.5 Additional Privacy or Information Security Details

Provide any other privacy or information security details here.

Section 27.6 Attestations

In the event of real or suspected breach of security, the Information Security Officer, Privacy Officer, VA Police (if appropriate), and the individual's supervisor will be notified within one hour of learning of the event.

Agree Disagree

Study staff will be up to date on any required VHA Privacy Policy and Information Security training or they will not be allowed access to VA Sensitive Information.

Agree Disagree

Access to research sensitive information, if any, will be removed when study personnel are no longer part of the research team.

Agree Disagree

At least one copy of all study records (whether sensitive or non-sensitive) will be retained under VA control and only destroyed in compliance with the approved Records Control Schedule

Agree Disagree

The VA retains ownership of the research data. Should the investigator leave the VA, custody of the research records will be assigned to another investigator and the Research Service notified in writing, or custody of the research records will be transferred to the Research Service.

Agree Disagree

Section 28 - Protocol Association to New or Existing Project

28) Is this a new R&D Project? Before you go on to complete the *Initial Review Submission Form* (which is used for attachments), please address the association of this Protocol to an R&D Committee Project. This Protocol may represent a new R&D Project, or it may be an additional Protocol under an existing R&D Project (such as when a single grant supports multiple Protocols). Will this Protocol be submitted to the R&D Committee as a new Project?

Yes No

Section 29 - Existing Project Association

29) The associated R&D Project should already exist in the database. Identify the R&D Project(s) that correspond to this protocol.

Project Status	Proposal Number	Project Title	Principal Investigator
Approved	1154731	1154731 Cognitive Rehabilitation in Individuals with Parkinson's Disease and Cognitive Impairment	[name]

The Protocol Application is now complete for a Protocol attached to an existing Project.

Next you will go on to the Initial Review Submission Form. This form is used to collect the Application and any other needed attachments for submission to the IRB for review.

Press *Save and Continue*
